APPENDIX A.1: Planned laboratory tests	64
Appendix B. Definitions for Adverse Events Monitoring	65
APPENDIX C: Clinical adverse events to be monitored : Symptoms	66
APPENDIX D: LABORATORY VALUES	67
APPENDIX E. FEVER SEVERITY GRADING	69

LIST OF ABBREVIATIONS

[figure not shown]
AE	Adverse Event
CFR	Code of Federal Regulations
CIOMS	Council for International Organizations of Medical Sciences
CONSORT	Consolidated Standards of Reporting Trials
CRF	Case Report Form
DSMB	Data and Safety Monitoring Board
DSMP	Data Safety Monitoring Plan
EC	Ethics Committee
FWA	Federal-Wide Assurance
GCP	Good Clinical Practice
IATA	International Air Transit Association
ICH	International Conference on Harmonisation
IND	Investigational New Drug Application
INS	Peruvian National Institute of Health (Instituto Nacional de Salud)
IRB	Institutional Review Board
CITI	Collaborative Institutional Training Initiative
LR or Lr	Lactobacillus reuteri
MOP	Manual of Procedures
NIDDK	National Institute of Diabetes and Digestive and Kidney Diseases
NIH	National Institutes of Health
OHRP	Office for Human Research Protections
OHSR	Office of Human Subjects Research
PI	Principal Investigator
PID	Personal Identifying Code
PL	Placebo
QA	Quality Assurance
QC	Quality Control
SAE	Serious Adverse Event
SID	Specimen identification code
SOP	Standard Operating Procedure
WHO	World Health Organization

PROTOCOL SUMMARY

Title:	Safety of Lactobacillus reuteri in healthy children aged 2-24 months
Précis:	Phase I double blinded randomized trial of the safety and tolerability of Lactobacillus reuteri DSM 17938 given for five successive days in healthy children. Sixty children will receive study product at a treatment to placebo ratio of 2:1 and followed for 3 months for safety outcomes.
Objectives:	
Primary: To assess the safety and tolerability of Lactobacillus reuteri (Lr) strain DSM 17938 in healthy infants and children. Safety will be assessed through the evaluation of adverse effects in both study arms for 90 days following product administration and by laboratory monitoring of CBC, AST, ALT, T. bilirubin, BUN and creatinine prior to product or placebo administration with follow-up assessment at 5 and 28 days. Tolerability will be assessed based on parental report of subjective symptoms of well-being during product administration and thru D28 of the study.
 
Secondary: To evaluate the duration of shedding of Lactobacillus reuteri (Lr) strain DSM 17938 following administration. This will be determined by and endpoint PCR assay for L. reuteri done on stool collected on D3, D5, D12, D15, D18, D24, D28, D36 on all participants.

Population:	The sample size of sixty is expected to include an equal number of healthy boys and girls 2-24 months of age at the time of enrollment from a rural community in Loreto Peru where chronic undernutrition and diarrheal disease are both highly prevalent.
Phase:	I
Number of Sites:	Single site- Loreto, Peru
Study Duration:	7 months
Subject Participation Duration:	3 months
Description of Agent or Intervention:	
1. Active Product: Description Lactobacillus reuteri 17938 suspended in sunflower oil, medium chain triglyceride oil, silicone dioxide. Total viable count of L. reuteri 17938 1×10^8 CFU/5 drops per day for 5 consecutive days
 
2. Placebo: Composition Sunflower oil, medium chain triglyceride oil and silicon dioxide. Total viable count of L. reuteri is zero CFU/ 5 drops.

Estimated Time to Complete Enrollment:	4 months

Schematic of Study Design:

2 INTRODUCTION: BACKGROUND INFORMATION AND SCIENTIFIC RATIONALE

2.1 Background Information

9 Probiotic therapy is intrinsically inexpensive and readily applicable in resource-poor
10 developing countries. Because of already published trials showing efficacy in the
11 treatment of diarrheal diseases, probiotic organisms such as *L. reuteri* are already in
12 clinical use for the treatment of acute infectious diarrhea^{1,2}, infantile colic,^{3,4} and atopic
13 disease.⁵ However, the avoidance of the formal IND process and FDA observed clinical
14 trials has compromised the credibility of many of these reports. There is substantial
15 evidence that the quality of preparations in distribution is highly variable and labels do not
16 always reflect true contents of marketed materials.⁶⁻⁸

18 Our long term goal is to develop *Lactobacillus reuteri* DSM 17398 as a safe and effective
19 therapy for acute infectious diarrhea in children. We have completed a Phase 1 trial in
20 adults⁹ ((NCT00774163) and are in the process of completing a Phase 1 study of children
21 ages 2-5 years with this product under IND ((NCT020124122). This study is designed to
22 provide evidence of the safety of the study product in well children in Peru under
23 demanding international quality standards. The study will not be done under IND but will
24 be done with extensive oversight by the study team in collaboration with NIDDK and a
25 DSMB. If shown to be efficacious in phase II/III trials we believe this will allow for the
26 greater use and acceptance of this product as part of the public health response to the
27 management of acute infectious diarrhea in children.

2.2 Rationale

33 We hypothesize that *L. reuteri* given at a dose of 1×10^8 CFU/ day is safe in infants in
34 children and likely to be beneficial in shortening the duration of episodes of diarrhea in
35 children in resource constrained settings.

37 BioGaia has chosen the dose level of 1×10^8 CFU/day for *L. reuteri* in man as a safe
38 and efficacious dose. The same dose is recommended for all ages.

39 Unlike pharmaceuticals, where doses are absorbed and metabolized, *Lactobacillus reuteri*
40 consists of live cells that become active and multiply along the entire digestive tract.
41 Whether in adults, children or infants, *Lactobacillus reuteri* grows from the initial dose to
42 colonize the available gut mucosa and thus, even though the surface area of the GI tract
43 differs with age, the substrates for multiplication are not limiting and thus the same dose is
44 effective.

1
2 The recommended daily dose of 1×10^8 CFU has shown efficacy in 10 studies on
3 prevention or treatment of symptoms.^{3,10-13}

4
5 Doses in the range of 10^8 – 10^9 CFU/day have shown efficacy in studies by: Eom 2005
6 (2×10^8),¹⁴ Valeur 2004 (4×10^8),¹⁵ Ouwehand 2002 (7×10^8).¹⁶

7
8 Some early studies in humans used higher doses up to 10^{10-11} CFU/day,^{1,2,17} primarily in
9 safety studies in young children, adults and immunocompromised adults (HIV-positive).
10 Blood, urinary, fecal and clinical parameters showed such higher levels to be safe. The
11 only possible side effect observed was a mild, and temporary, increase in flatulence.

12
13 Studies performed with lower than the recommended 1×10^8 CFU dose demonstrated gut
14 colonization, but some of studies demonstrated less optimal effect for prevention or
15 treatment of diarrhea. The 1×10^5 and 1×10^7 dosages both colonized the gut and had
16 significant effect on watery stools in newborns. 1×10^7 CFU/day had significant effect on
17 frequency of diarrhea and close to significant effect on duration of watery diarrhea in
18 rotavirus gastroenteritis.²

19
20 The five day treatment period is based on clinical studies that generally showed biologic
21 response with 24-48 hours. Shorter duration of therapy is preferred as it is more
22 practical to implement and limits cost per treatment making this treatment a feasible
23 option for a common important public health problem.

24
25 **2.3 Potential Risks and Benefits**

26
27 *Potential Risks*

28 There are slightly greater than minimal risks associated with study participation. Blood
29 draws have a slight risk of bruising or infection. Health workers are trained in phlebotomy.
30 The prospective surveillance portion involves the limited inconvenience of daily interviews
31 to obtain symptom and illness histories. There also exists a small risk that the information
32 collected may not remain confidential, however, the data collected is not of a sensitive
33 nature and would be unlikely to have important social or legal consequences for the
34 participant and his or her family. Each enrollment in the study involves the risk associated
35 with the possible consumption of the probiotic *Lactobacillus reuteri*. Although there is
36 extensive worldwide use of these products, it is possible that their ingestion could lead to
37 complications, including sepsis.^{18,19} As we have cited numerous studies where these
38 probiotics have been used for both treatment and prophylaxis of diarrhea in children
39 without serious adverse effects, we believe the risk is very small. We will monitor closely
40 for adverse events and address them promptly with appropriate medical interventions,
41 which will be supplied by the study.

42
43 *Benefits*

44 It is not believed that subjects will receive any health benefit related to participation in the
45 study. Parents may only perceive that they are contributing to the evaluation of a
46 treatment of diarrhea that may be important in the future.

1
2 **2.3.1 Potential Risks**
3

4 The major potential risk associated with the administration of probiotics is the rare
5 disseminated bloodstream or deep tissue infection with the probiotic strain or the
6 contamination of the probiotic product with a pathogen or toxin. Bloodstream infection,
7 liver abscesses, and joint infections have occurred with probiotic bacteria, predominantly
8 *Lactobacillus rhamnosus* GG, although there have been reports of *L. acidophilus*
9 bacteremia associated with product ingestion.^{18,20-23} Additionally recently intestinal
10 mucormycosis caused by the contamination of probiotic preparation ABC Dophilus
11 powder which contains *B. lactis*, *S. thermophilus*, and *L. rhamnosus* was found to be
12 contaminated with *Rhizopus oryzae* which lead to the death of one infant in Connecticut in
13 2014.²⁴

14
15 To mitigate this risk we have taken several precautions. We have chosen a product that
16 was isolated by the current provider who can trace the origin and any changes in the
17 product, a standard almost no other product with demonstrated efficacy in treating acute
18 enteric infections can meet. This product was derived from a strain isolated in human
19 breastmilk in Peru by scientists at BioGaia who have held this reference strain since that
20 time.²⁵ We have also chosen a product that has no documented cases in Pubmed
21 (Reviewed Feb 20th, 2015) of disseminated bloodstream infections or deep tissue
22 infections despite the distribution of the product in the US and Europe since 2007. The
23 derivative strain *Lactobacillus reuteri* 55730 (different from the product strain only because
24 it had additional plasmids that contained antibiotic resistance genes) was previously
25 distributed for 10 years and taken together millions of doses of these two highly related
26 products have been sold with no reports in the literature of bacteremia or deep tissue
27 infection and no product contamination concerns. This product has been evaluated in
28 several clinical trials^{26,27} including ones done in infants, with no safety concerns, including
29 studies that gave it at the study dose daily to prevent necrotizing enterocolitis in low birth
30 weight newborns,^{28,29} and in infants with colic.³⁰⁻³⁵ Furthermore, as detailed in our product
31 assurance plan, we will rigorously run independent assessments of the viability and
32 identity of the product provided by our probiotic supplier which will further mitigate risk to
33 subjects in compliance with CBER guidance on early clinical trials and provide a high
34 standard for the evaluation of probiotic products by other investigators.

35
36 Evidence on the safety and history of the product strain are available in Appendix F.
37
38

39 **2.3.2 Known Potential Benefits**
40
41

42 There are no direct benefits to subjects who participate in this study. Potential benefits of
43 this product in other studies have shown it efficacious in the treatment of infantile colic,⁴
44 the prevention and treatment of acute infectious diarrhea,² and the prevention of
45 necrotizing enterocolitis in low birth weight babies.²⁹

7
8
9
10

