3.2.1 Primary Outcome Measures

23
24 There are three major areas of safety and tolerability that will be assessed in this phase I
25 trial. The outcome measurements will be compared between the two treatment groups
(Intervention v placebo) with intent to treat analysis.

26
27
28 **1. Evidence of invasive infection resulting from the administration of *L. reuteri* DSM
29 17938.** Baseline and daily temperature measurements will be made during the study
30 period. Complete hemogram with differential count obtained at baseline, on day 5, and
31 on day 28. Vital signs will be monitored daily during the administration of the treatment
32 (days 1-5). The evaluation of all febrile episodes will be done and include a physician
33 exam and the evaluation of blood smears for malaria and blood cultures for the
34 evaluation of possible bacteremia.

35
36 Specific outcome parameters in this category include:

37
38 a. Mean daily temperature
39 b. Incidence of fever on study days 1-5
40 c. Frequency of temperature readings categorized as fever (adjusted for number of
41 subjects per group)
42 d. Number of episodes of *L. reuteri* bacteremia

43
44 **2. Clinical tolerance.** The inclusion of a placebo group will allow for comparisons of daily
45 symptom measurements to be compared between the treatment and placebo group.
The symptoms will be monitored for at household visits, and will be graded as
adverse events according to defined criteria. Symptoms monitored as AEs include
fever, nausea/upset stomach, vomiting, diarrhea, irritability, rash, pruritis, and
wheezing or bronchospasm. Diagnostic microbiology will be performed on all stool
specimens from subjects who develop diarrhea during the 90 days following initiation
of therapy.

46
47 Specific outcome parameters in this category include:

- 1 a. Frequency and severity of symptoms monitored as AEs (adjusted for number of
2 subjects per group)
- 3 b. Frequency of all AEs (adjusted for number of subjects per group)
- 4 c. Frequency of SAEs (adjusted for number of subjects per group)

5

6

7 **3. Evidence of toxicity resulting from the *L. reuteri* DSM 17938 preparation.**

8 Participants will have baseline, day 5, and day 28 assessment of hematologic status and
9 renal and hepatic function. Assessment of renal function will include blood urea nitrogen
10 (BUN) and creatinine (Cr). Assessment of hepatic toxicity will include transaminases

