4 STUDY DESIGN

The study is a single center Phase 1 double blind placebo controlled trial of *Lactobacillus reuteri* DSM 17938 in children aged 2-24 months. The study population is based in a community with a registered clinical trial center in rural Peru where this protocol can be done in a highly controlled setting. The study is intended to enroll healthy children living in a resource constrained setting where chronic undernutrition and diarrheal disease is common, as this is the population that is most likely to receive benefit from the use of this and or other probiotic products for the treatment of acute infectious diarrhea and environmental enteropathy.

Up to 100 subjects will be enrolled in order to obtain the randomization of 60 subjects, who will receive study product or placebo at a ratio of 2:1. Participants will be enrolled between the ages of 8 weeks and 24 months. There will be no age stratification. Participants will be screened with a baseline history and physical examination and laboratory tests to determine the HIV status of the child, as well baseline laboratory tests to evaluate occult infections, hepatic function, and renal function. Upon randomization subjects will be screened and randomized to a treatment arm. Product will be administered under the direct supervision of study staff daily for 5 days. The primary outcome is the safety and tolerability of the product at this dose and formulation. Safety will be assessed by the monitoring of baseline laboratory tests at 5 and 28 days following the initiation of therapy and by AE monitoring. Tolerability will be evaluated by analyzing 28 day diary cards that are distributed to all randomized subjects on which parents record their child's symptoms (specifically fever, anorexia/oral intake, vomiting, diarrhea, irritability, rash, wheezing, or open fields which allows them to describe any issue their child may experience and grade its severity). Secondary outcomes include: 1) The assessment of the duration of shedding of *Lactobacillus reuteri* (Lr) strain DSM 17938 following administration. This will be determined by and endpoint PCR assay for *L. reuteri* done on stool collected on D3, D5, D12, D15, D18, D24, D28, D36 on all participants.

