9 ASSESSMENT OF SAFETY

9.1 Specification of Safety Parameters

1. Evidence of invasive infection resulting from the administration of *L. reuteri* DSM 17938. Baseline and daily temperature measurements will be made during the study period. Complete hemogram with differential count obtained at baseline, on day 5, and on day 28. Vital signs will be monitored daily during the administration of the treatment (days 1-5). The evaluation of all febrile episodes will be done and include a physician exam and the evaluation of blood smears for malaria and blood cultures for the evaluation of possible bacteremia.

2. Clinical tolerance. The inclusion of a placebo group will allow for comparisons of daily symptom measurements to be compared between the treatment and placebo group. The symptoms will be monitored for at household visits, and will be graded as adverse events according to defined criteria.

Symptoms monitored as AEs include fever, vomiting, diarrhea, irritability, rash, pruritis, and wheezing or bronchospasm. Diagnostic microbiology will be performed on all stool specimens from subjects who develop diarrhea during the 90 days following initiation of therapy.

3. Evidence of toxicity resulting from the *L. reuteri* DSM 17938 preparation.

Participants will have baseline, day 5, and day 28 assessment of hematologic status and renal and hepatic function. Assessment of renal function will include blood urea nitrogen (BUN) and creatinine (Cr). Assessment of hepatic toxicity will include transaminases (AST, ALT) and total bilirubin. Hematologic status will be determined by CBC to measure hemoglobin and absolute leucocyte count.

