11.1 Study Hypotheses and Analysis

A. The primary hypotheses are that *L. reuteri* therapy at the specified dose is safe and well-tolerated in children aged 2-24 months. There are three areas of safety and tolerability that will be assessed in this Phase 1 trial.

- 1. Evidence of bacteremia or invasive infection resulting from the administration of *L. reuteri* 17938.** Baseline and daily temperature measurements will be made during the study period during the product administration phase and then on all scheduled home visits. Complete blood counts with differential counts will be obtained at baseline, on day 5, and on day 28. The evaluation of all documented febrile episodes will include an examination by a physician, and thick smear for malaria, and blood culture for the evaluation of bacteremia if the temperature is greater than 39°C using temporal artery probe measures.

Specific outcome parameters in this category include:

- a. Mean daily temperature
- b. Incidence of fever on study days 1-5
- c. Frequency of temperature readings categorized as fever (adjusted for number of subjects per group)
- d. Number of episodes of *L. reuteri* bacteremia

2. Evidence of toxicity resulting from the *L. reuteri* DSM 17938 preparation.
Participants will have baseline, day 5, and day 28 assessment of hematologic status and

1 renal and hepatic function. Assessment of renal function will include blood urea nitrogen
2 (BUN) and creatinine (Cr). Assessment of hepatotoxicity will include transaminases
3 (AST, ALT) and total bilirubin. Hematologic status will be determined by CBC to
4 measure hemoglobin count and absolute neutrophil count, as mentioned above.

5
6 Specific outcome parameters in this category include:

7
8 a. Mean values for laboratory tests monitored (adjusted for number of subjects per
9 group). These are listed in Appendix D.
10 b. Frequency of out of range values for laboratory tests monitored (adjusted for number
11 of subjects per group). These are listed in Appendix D.

12
13 2. **Clinical tolerance.** The inclusion of a placebo group will allow for comparisons of the
14 prevalence of daily symptom measurements between treatment groups. The
15 symptoms monitored on the daily diary card (fever, anorexia/decreased oral intake,
16 vomiting, diarrhea, irritability, rash, itching, wheezing) are graded by the parent(s) of
17 the participant as mild, moderate, severe, or very severe. Parents report of severity

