APPENDIX C: Clinical adverse events to be monitored : Symptoms*

Systemic (General)	Mild (Grade 1)	Moderate (Grade 2)	Severe (Grade 3)	Potentially Life Threatening (Grade 4)
1. Altered feeding/Anorexia	Mild	Moderate—decreased oral intake	Severe—little oral intake	Unable to ingest food or fluid for more than 24 hours
2. Vomiting	1 episode/24 hours	2-3 episodes/24 hours	4-6 episodes/24 hours	> 6 episodes/24 hours or hypotensive shock
2. Diarrhea	3 liquid stools per 24 hours	4 liquid stools per 24 hours	Liquid stools, 5-8 per 24 hours	Liquid stools, > 8 per 24 hours, or requires hospitalization
4. Irritability	Slightly irritable, no interference with activity	Moderately irritable, some interference with activity	Significant; prevents daily activity or seeks medical attention	Incapacitating or requires hospitalization
5. Rash	Localized macular rash	Diffuse macular, maculopapular, or morbilliform rash	Grade 2 rash with vesicles, bullae, ulcerations, target lesions, or angioedema	Severe generalized rashes (e.g. Stevens Johnson syndrome, toxic epidermal necrolysis)
6. Pruritis	Localized itching, relieved spontaneously or in > 48 hours	Localized itching lasting 48 hours or longer	Generalized itching	Generalized, severe itching or generalized itching lasting > 48 hours
7. Bronchospasm or wheezing	Mild wheezing, or minimal increase in respiratory rate	Wheezing with nasal flaring, intercostal retractions, or pulse oximetry 90-95%	Wheezing with dyspnea at rest, inability to perform normal activities, or pulse oximetry <90%	Respiratory failure or anaphylaxis

* Based on NIAID Division of AIDS Table for Grading the Severity of Adult and Pediatric Adverse Events, December 2004
<http://www.niaid.nih.gov/labsandresources/resources/daidsclinrsrch/documents/daidsaegradingtable.pdf>

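### Flatulence, named in section 2.2 as the only possible side effect in early higher-dose studies, is on no solicited symptom list; it reaches the primary tolerability outcome only if volunteered, and with no settled grading rule.

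*Combined protocol and SAP*

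**What the plan says.** Section 2.2 introduces the evidence with "Some early studies in humans used higher doses up to" 10^10-11 CFU/day, places it mainly in safety studies of young children, adults and HIV-positive adults, and concludes that the "only possible side effect observed was a mild, and temporary, increase in flatulence".

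Tolerability is part of the primary objective. Under clinical tolerance, sections 3.2.1 and 11.1 give three parameters: 2a, frequency and severity of the symptoms monitored as AEs; 2b, frequency of all AEs; 2c, frequency of SAEs.

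The symptoms asked about are listed in six places:

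- Section 3.2.1: "fever, nausea/upset stomach, vomiting, diarrhea, irritability, rash, pruritis, and" wheezing or bronchospasm. The expected AEs in section 9.2.1 are the same.
- Section 9.1: "Symptoms monitored as AEs include fever, vomiting, diarrhea, irritability, rash, pruritis, and wheezing or bronchospasm".
- Section 4, diary card: "fever, anorexia/oral intake, vomiting, diarrhea, irritability, rash, wheezing, or open fields" in which the parent may describe and grade anything else.
- Section 11.1: "symptoms monitored on the daily diary card (fever, anorexia/decreased oral intake", then vomiting, diarrhea, irritability, rash, itching and wheezing, each graded by the parent from mild to very severe.
- Appendix C, "Clinical adverse events to be monitored : Symptoms": seven graded items, beginning with "Altered feeding/Anorexia".

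Unlisted events have other routes in. Section 7.4 has parents record unsolicited AEs on the diary and field workers verify them. Section 9.2.1 gives field workers an open-ended space for other symptoms possibly related to the probiotic, and a general question about medical problems at each visit.

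**The concern.** A tolerability assessment normally asks directly about any reaction that earlier experience has raised. Here the protocol raises one, and every list leaves it out. The listed symptoms are, in section 9.2.1's own description, common in this population, so most of what 2a counts will be background illness.

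An unsolicited symptom depends on a parent thinking it worth mentioning. Gas in an infant may not strike a parent as a medical problem, or a field worker as a possible probiotic effect. A conclusion that the product is well tolerated would then rest partly on silence about a symptom nobody was asked about. The information cannot be recovered once the diaries are collected.

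**Working it through.** **Step 1. Compare the lists.** Items on which they differ, plus gas:

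| Place | Nausea/upset stomach | Anorexia/feeding | Itching | Flatulence/gas |
|---|---|---|---|---|
| 3.2.1 | yes | no | yes | no |
| 4 (diary) | no | yes | no | no |
| 9.1 | no | no | yes | no |
| 9.2.1 (expected AEs) | yes | no | yes | no |
| 11.1 (diary) | no | yes | yes | no |
| Appendix C | no | yes | yes | no |

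Gas is absent throughout. The nearest items, upset stomach and irritability, do not measure it. The lists also disagree with one another.

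**Step 2. Trace a case of flatulence.** It does not enter 2a. If volunteered, it is an AE and enters 2b. Section 11.1 counts each subject once per AE, so a separate line for flatulence is possible, but only from volunteered reports.

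**Step 3. Trace its severity.** Section 7.4 says AEs outside Appendices C, D and E are reported without a grade, and section 9.2.1 says the same of AEs outside the toxicity table. Section 9.2.1 then gives a generic Level 1-4 scale for events outside the protocol's grading system, and section 4 lets parents grade open-field entries. These rules conflict.

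**Step 4. Illustrate the size.** The plan gives no figure to reproduce: section 11.2 bases the sample size on precedent, with no event rate or power. The only input from the documents is 60 children at 2:1, so 60 × 2/3 = 40 active and 60 × 1/3 = 20 placebo. The rates and capture fractions below are assumptions.

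Expected reports = n × true rate × capture c. Observed difference = c × (0.30 − 0.10).

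| Capture c | Active, 40 × 0.30 × c | Placebo, 20 × 0.10 × c | Difference | Fisher exact power, two-sided 0.05 |
|---|---|---|---|---|
| 90% | 10.8 | 1.8 | 18 points | about 32% |
| 30% | 3.6 | 0.6 | 6 points | about 1% |
| 10% | 1.2 | 0.2 | 2 points | about 0% |

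At 10% capture, the chance of no report at all in the active arm is (1 − 0.03)^40 ≈ 0.30.

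Normal-approximation check at 90% capture (27% v 9%):

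- pooled rate = (10.8 + 1.8)/60 = 0.21
- null SE = √[0.21 × 0.79 × (1/40 + 1/20)] = 0.1115
- alternative SE = √(0.27 × 0.73/40 + 0.09 × 0.91/20) = 0.0950
- power = Φ[(0.18 − 1.96 × 0.1115)/0.0950] = Φ(−0.41) ≈ 34%

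Other assumed rates, same approximation, at full, half and quarter capture: 10% v 40% gives 70%, 30% and 13%; 20% v 50% gives 62%, 25% and 11%. Capture matters in every case, but only a large true difference would be reasonably powered even with full capture.

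**The case against.** A reader might infer that the primary tolerability outcome does not measure flatulence at all. The documents do not support that. Parameter 2b counts every AE, and there are three passive routes in: the diary open field, the field worker's open-ended record and the general question at each visit. All treatment-emergent AEs also go to the DSMB in closed session. This objection stands: the gap is in soliciting and grading, not in whether a case can count.

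A reader might also take flatulence as an established effect of this product at this dose. Section 2.2 says possible, calls it mild and temporary, and refers to doses up to 10^10-11 CFU/day, which is 100 to 1,000 times the labelled 10^8. Section 2.3.1 names invasive infection and contamination as the major risks and cites infant studies without safety concerns. This also stands, and it keeps the point modest. It does not remove it: the early studies included young children, and section 2.2 itself argues that the organism multiplies from the initial dose, so the protocol's own reasoning does not rule out a gut effect at a lower dose.

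Finally, a solicited item would not make an excess statistically detectable. That is correct under the main assumed rates; power stays near one third. The trial is summarised descriptively, so the relevant gain is a usable rate in each arm.

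**Conclusion.** The point holds as a moderate measurement gap in a primary outcome. The one possible side effect that section 2.2 takes from earlier studies is not solicited, falls outside 2a, depends on volunteered reports under 2b, and has no settled severity rule. Those statements rest on the text alone.

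That under-reporting is likely is a judgement; its extent is unknown, and the counts above depend on assumed rates and capture fractions. It would go too far to say that a real excess would be missed because the item is absent and found if it were present: under the 30% v 10% assumption, a significant difference is unlikely either way. What is lost is a placebo-compared description of how often gas occurs and how severe it is.

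**What to change.** Before the forms are printed:

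1. Add one solicited item, flatulence/gas, to the diary card and the visit symptom form, graded on the mild-to-very-severe parent scale already in section 11.1. Name it in 3.2.1 and 11.1 and report its frequency and severity by arm under 2a.
2. Do not simply add a row to Appendix C. Section 7.3 bars candidates with any current Appendix C event and stops randomization if an exclusionary event develops during screening. Exclusion criterion 6 in section 5.2 covers pre-existing monitored AEs, and section 5.4.3 makes meeting an exclusion criterion (out-of-range laboratory values excepted) a reason for discontinuation. Because criterion 6 is worded around monitored events, keeping the item out of Appendix C may not be enough; the sponsor should state how it relates to each of these sections.
3. Reconcile the grading rule for unlisted AEs across sections 4, 7.4 and 9.2.1. As written, section 7.4 would leave an item outside the appendices ungraded.
4. Reconcile the six symptom lists into one.

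The cost is one diary line, one form field and text edits that the conflicting lists need anyway. The downside is more mild reports in both arms, since gas can be expected in infants regardless of treatment; the placebo arm provides the comparison.
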